4.4 Randomized intervention

The randomized interventions will be the following (in random order, separated by a 1-week washout period)

[figure not shown]
(A) Potassium nitrate: Potassium nitrate crystals will be purchased and placed into oral gelatin capsules with an inert filler (lactose monohydrate). Capsules will be prepared at the University of Pennsylvania Investigational Drug Service [[name]]. Each capsule will contain 610 mg KNO₃-, corresponding to 6.03 mmoles of NO₃-, plus 190mg of lactose monohydrate, spray dried, NF. The dose for this trial will be 18 mmoles of NO₃-per day, given as one capsule (6 mmoles) three times a day.

(B) Control drug: For the purpose of conducting this clinical trial, a control capsule will be made consisting of potassium chloride, granular, USP (450mg) plus lactose monohydrate, spray dried, NF (300mg) combined and packed into an identical capsule shell. We chose potassium chloride in order to isolate the effects of nitrate from any potential effect of potassium supplementation. The dose for this trial will be 18 mmoles of KCI per day, given as one capsule (6 mmoles) three times a day.

5. STUDY VISITS AND PROCEDURES

A letter may be sent to potential subjects prior to initial contact. An overview of the study design and flow of study visits is presented in Figure 4.

Figure 4. Overview of the study design and procedures.

Not performed for subjects enrolled at the NW site

The following investigational devices will be used during the study:

- Aurora device: wearable pulse collection device (watch)
- Portalite: continuous wave near infrared spectroscopy (NIRS) system to measure oxygenation of muscle tissue
- Portamon: continuous wave near infrared spectroscopy (NIRS) system to measure oxygenation of muscle tissue

5.1. Initial Visit

During the baseline study visit, inclusion and exclusion criteria will be reviewed to ensure subject suitability. After subject eligibility is confirmed, written informed consent will be obtained from the subject using Institutional Review Board (IRB)-approved documents. Informed consent will be obtained before any study procedures. Subjects will be given the opportunity to have all questions regarding their participation answered in detail in a private setting before entering the study. Informed consent may be obtained in-person or virtually.

Following informed consent, a physical examination, with measurement of orthostatic blood pressures, will be performed. A urine pregnancy test will be performed in women with childbearing

potential. Blood will be collected for measurement of (a) comprehensive metabolic panel; (b) complete blood count; (c) NT-pro-BNP; and (d) methemoglobin. A pregnancy test (women of childbearing potential) and Glucose-6-phosphate dehydrogenase (G6PD) deficiency screening (males of males of African, Asian or Mediterranean decent) will be performed as needed. Blood, urine, and saliva samples will be collected and frozen for nitrate/nitrite level determination. Following the collection of baseline labs and biomarker samples, subjects will be provided with a standard low nitrate breakfast. The Kansas City Cardiomyopathy Questionnaire (KCCQ) will be administered. Subjects will also be given an informational brochure regarding foods that are high in nitrate/nitrite and will be instructed to avoid such foods while participating in the study.

Computerized cognitive assessment testing will be performed using cogstate software (Cogstate: New Haven, CT). The assessment includes a customized battery of seven tests that measure various cognitive domains. The battery includes the following tests:

- International Shopping List Test
- Gorton Maze Learning Test
- Detection Test
- Identification Test
- One Card Learning Test
- One Back Test
- International Shopping List Test- Delayed Recall (memory)

The system works with an internet server administered and maintained by Cogstate, which quantifies the subject's performance/responses and calculates cognitive scores. No personal identifiable information will be entered/uploaded into the server.

Echocardiography will then be performed using a standardized protocol. Images will be obtained from the parasternal long axis, short axis, apical 5-, 4-, 3-, and 2-chamber, subcostal, and suprasternal views for offline analysis of myocardial strain. Dedicated ventricular chamber images will be obtained in the 4- and 2-chamber apical positions for determination of left ventricular volumes. Mitral inflow velocities, including color M-mode interrogation, will be assessed in the 4- chamber view. Tissue Doppler imaging will be performed at the mitral septal position, approximately 1-cm apical to the mitral valve plane. Additional images will be obtained in the parasternal short axis at the level of the papillary muscles, 2-chamber, and 4-chamber apical views for assessment of myocardial strain. Pulse-wave Doppler interrogation of the left ventricular outflow tract (LVOT) will be performed in the apical 5-chamber view.

Concurrent arterial tonometry will be performed using a high-fidelity tonometer at the carotid, femoral, and radial arteries, using a Sphygmocor device. Waveforms will be calibrated using the brachial artery blood pressures, obtained using a validated oscillometric device. Waveforms will be digitally-stored for off-line analysis. Where available, we will also measure blood pressure using a BP+ device (Uscom, Sydney, Australia), which is an FDA-approved device that measures brachial and central blood pressure using a standard brachial blood pressure cuff. Body surface measurements will be made to determine distance between the suprasternal notch to the carotid, radial, and femoral arteries. A 6-minute walk test will also be performed during this visit. Patients who demonstrate significant desaturation during exercise (<=94% or a fall in Spo2 >= 5%) will be excluded from the study

Initial Visit Procedures

- Informed Consent ^a
- Eligibility assessment
- Medical History, Concomitant Medications
- Dietary counseling
- KCCQ
- •Physical Exam (including orthostatic vital signs and anthropometric measurements)

•ECG, Laboratory tests (CBC, comprehensive metabolic panel, NTproBNP or proBNP, methemoglobin; pregnancy test and G6PD deficiency screening as needed)

- Blood, urine and saliva collection
- Cognitive assessment
- 2D echocardiogram, arterial tonometry
- Device (Aurora and Actigraph) education
- 6 minute walk test with O₂ saturation and Aurora device

^a Informed consent will be obtained before any study procedures

5.2. Randomization procedure

A stratified blocked randomization will be performed based on enrollment site (UPenn/Northwestern/ VAMC), sex, and ethnicity. A sufficient number of complete blocks will be generated for each stratum so that randomized assignments are available for every eligible subject. Strata-specific treatment order assignments and will be provided by a member of the data management team. Each block will contain an equal number of allocations to KNO₃ followed by KCI versus KCL followed by KNO₃. The order of treatment sequences within each block will be randomized.

To preserve blinding, the strata-specific treatment order assignments and the associated studyspecific patient identification number will be provided to each study IDS representative site in electronic format (excel spreadsheet) pre-sealed envelopes.

Upon determination of subject eligibility into the trial, the IDS representative will break the seal of the next envelope for the appropriate stratum to determine the treatment group assignment based on the appropriate stratum-specific scheme and will record the patient identification number for that study subject.

5.3. Intervention Phase 1

Subjects will be randomized to either active drug (KNO₃) or placebo (KCI) as the "first" drug for phase A. The initial dose will be one 6 mmol capsule administered twice daily, to be taken with meals. We will provide subjects with a 14-day supply of study medication to account for potential delays in the shipment of the 2^{nd} batch of medication (i.e., after the 1-week call).

1-week call: Subjects will be called by telephone ~1 week later for side-effect assessment. Subjects will receive reinforcement of the dietary restrictions imposed during the study. Subjects will be interrogated about headaches and dizziness. If these symptoms are not present, or are not worse compared to the subject's baseline, the drug dose will be up titrated to 18 mmol daily (One 6-mmol capsule taken 3 times per day). The presence of orthostatic symptoms (i.e. sustained lightheadedness upon standing) will prompt a visit to assess for orthostatic vital signs. The presence of symptomatic orthostatic hypotension (20 mmHg reduction in systolic blood pressure with associated symptoms such as dizziness) will prompt exclusion of patients from the trial.

Subjects may experience symptoms upon dose uptitration that do not prompt exclusion from the trial, as per the criteria noted above (for example, but not limited to, mild dizziness, gastrointestinal symptoms, fatigue). In these instances, the Site Principal Investigator can reduce the dose back to 6-mmol capsule taken twice per day, for the remainder of the treatment phase. For subjects who have a baseline serum K between 4.7 and 5.0 mEq/L in the presence of either: (a) potassium-sparing diuretic use, or (b) estimated glomerular filtration rate of 30-39 mL/min/1.73m², we will check a serum potassium 1 week after the implementation of the 18 mmol/d dose as a safety measure. A serum potassium >5.5 mEq/L will prompt exclusion at this point.

At approximately 5 weeks into each interventional phase, the Aurora and Actigraph devices will be given to the subjects. The goal will be for the subjects to wear these devices during the final week of each interventional phase to look for differences with each therapy. The devices will be brought back by the subject at his/her next visit.

6-week endpoint assessment: Following ~6-weeks of therapy with KNO₃/KCI, subjects will return for endpoint assessments. Physical examination with measurement of orthostatic blood pressure, pill count, KCCQ, dietary counseling, cognitive assessment, and side effect assessments will be performed. A urine pregnancy test will be performed in women with childbearing potential. An intravenous catheter will be placed in the antecubital vein and securely fixed in place. Blood, urine, and saliva samples will be collected prior to, and approximately 2 hours after the morning dose administration, given with a standardized low-nitrate breakfast. Blood RNA samples will be collected prior to the morning dose administration using Paxgene tubes (BD Biosciences, Franklin Lakes, NJ). Subjects will then undergo repeat echocardiography, arterial tonometry, and blood pressure measurements (including BP+ central blood pressure measurements). Subjects will then perform a maximal-effort peak oxygen consumption (VO₂) test using a supine bicycle exercise test with expired gas analysis. Cardiac output at rest will be measured immediately prior to exercise using pulsed wave Doppler echocardiography. Exercise cardiac outputs will also be obtained using the same technique. An additional blood sample will be obtained at peak exercise. The Aurora watch will be worn during exercise when possible. Subjects enrolled at Penn or the VA will undergo an assessment of skeletal muscle mitochondrial oxidative capacity using MRI either before, or at least 3 hours after, peak VO₂ testing. Based on scheduling and availability, the MRI may be performed on a different day than the exercise study. The Kansas City Cardiomyopathy Questionnaire (KCCQ) will be administered.

Phase 1: 6-week Visit Procedures

• Interim medical history, concomitant medications

- Physical exam (including orthostatic vital signs)
- Pill count
- Blood, urine and sputum collection, blinded drug administration
- ECG, labs (CBC, comprehensive metabolic panel, methemoglobin, pregnancy test as needed, BD PAXgene RNA samples)
- KCCQ
- Blood, urine, and saliva collection approximately 2 hours post-administration
- Cognitive assessment
- 2D echocardiogram, arterial tonometry

•Cardiopulmonary test with resting and exercise cardiac output measurements, blood draw at peak exercise

- If feasible, plantar flexor exercise / MRI (fat/water imaging / Creatine CEST / PC-MRI); these measurements are not performed at the Northwestern site
- Data download of the Aurora device and Actigraph

Additional visit for subjects participating in the Cardiac MRI sub-study: Subjects who participate in the MPR ancillary study will undergo a cardiac MRI with regadenoson administration. This will be scheduled during the last 2 weeks of the study intervention (4-6 weeks after initiation of drug administration in Phase 1), such that it will not interfere with the scheduling of the main trial visits. The cardiac MRI may take place on a different day than the exercise study or the lower extremity MRI scan and may occur either before or after the exercise endpoint study visit.

5.4. 1-week washout period

Following the endpoint assessment, subjects will enter a 1-week washout period during which they will not receive any study medications.

5.5. Intervention Phase 2

Following the washout period, subjects will receive either active drug (KNO₃) or placebo (KCI) during phase 2 of the trial. Subjects will receive the intervention (KNO₃ or KCI) that was not administered in phase 1, such that each subject will receive both study interventions in this cross-over design. The ~1-week call and the ~6-week study visit will be repeated as above. We will provide subjects with a 14-day supply of study medication to account for potential delays in the shipment of the 2nd batch of medication (i.e., after the 1-week call).

1-week call: Subjects will be called by telephone ~1 week later for side-effect assessment. Subjects will receive reinforcement of the dietary restrictions imposed during the study. Subjects will be asked about headaches and dizziness. If these symptoms are not present, or are not different than the subject's baseline, the drug dose will be up-titrated to 18 mmol daily (One 6mmol capsule taken 3 times per day). The presence of orthostatic symptoms will prompt a visit to assess for orthostatic vital signs. The presence of symptomatic orthostatic hypotension (20 mmHg reduction in systolic blood pressure with associated symptoms such as dizziness) will prompt exclusion of patients from the trial.

Subjects may experience symptoms upon dose uptitration that do not prompt exclusion from the trial, as per the criteria noted above (for example, but not limited to, mild dizziness, gastrointestinal

symptoms, fatigue). In these instances, the Site Principal Investigator can reduce the dose back to 6-mmol capsule taken twice per day, for the remainder of the treatment phase.

At approximately 5 weeks into each interventional phase, the Aurora and Actigraph devices will be given to the subjects. The goal will be for the subjects to wear these devices during the final week of each interventional phase to look for differences with each therapy. The devices will be brought back by the subject at his/her next visit.

6-week endpoint assessment: Following ~6-weeks of therapy with KNO₃/KCl, subjects will return for a repeat endpoint assessment. Physical examination with measurement of orthostatic blood pressure, pill count, KCCQ, dietary counseling, cognitive assessment, and side effect assessments will be performed. A urine pregnancy test will be performed in women with childbearing potential. An intravenous catheter will be placed in the antecubital vein and securely fixed in place. Blood, urine, and saliva samples will be collected prior to, and approximately 2 hours after, morning dose administration, given with a standardized low-nitrate breakfast. Blood RNA samples will be collected prior to the morning dose administration using Paxgene tubes (BD Biosciences, Franklin Lakes, NJ). Subjects will then undergo repeat echocardiography, arterial tonometry, and blood pressure measurements (including BP+ central blood pressure measurements). Subjects will then perform a maximal-effort peak oxygen consumption (VO₂) test using a supine bicycle exercise test with expired gas analysis. Cardiac output at rest will be measured immediately prior to exercise using pulsed wave Doppler echocardiography. Exercise cardiac outputs will also be obtained using the same technique. An additional blood sample will be obtained at peak exercise. The Aurora watch will be worn during exercise when possible. Subjects enrolled at Penn or the VA will undergo repeat assessment of skeletal muscle mitochondrial oxidative capacity using MRI either before, or at least 3 hours after, peak VO_2 testing. Based on scheduling and availability, the MRI may be performed on a different day than the exercise study. The Kansas City Cardiomyopathy Questionnaire (KCCQ) will be administered. Following the final endpoint assessment, subjects' participation in the study will be over.

Phase 2: 6-Week Visit (final visit) Procedures

- Interim medical history, concomitant medications
- Physical exam (including orthostatic vital signs)
- Pill count and side effect assessment
- Blood, urine, and sputum measurements, followed by blinded drug administration
- ECG, labs (CBC, comprehensive metabolic panel, methemoglobin, pregnancy test as needed, BD PAXgene RNA samples)
- KCCQ
- Blood, urine and, saliva collection approximately 2 hours post-administration
- Cognitive assessment
- 2D echocardiogram, arterial tonometry
- Cardiopulmonary test with resting and exercise cardiac output measurements, blood draw at peak exercise
- If feasible, plantar flexor exercise / MRI (fat/water imaging / Creatine CEST / PC-MRI); these measurements are not performed at the Northwestern site
- Data download of the Aurora device and Actigraph

Additional visit for subjects participating in the Cardiac MRI Sub-study: Subjects who are to participate in cardiac MRI sub-study will undergo a Stress Cardiac MRI with regadenoson administration. This will be scheduled during the last 2 weeks of the study intervention (4-6 weeks after initiation of drug administration in phase 2), such that it will not interfere with the scheduling of the main trial visits. The cardiac MRI may take place on a different day than the exercise study or the lower extremity MRI scan and may be performed either after or before the exercise assessment.

5.6 Adverse Event Reporting

All adverse events will be reported following FDA guidelines. The research team will keep a log of all adverse events that occur in the trial, and any reportable events will be reported per Section 7 in this protocol. The study team in charge of the conduct of the trial is up to date on all trainings pertaining to safety guidelines and adverse event reporting. Adverse Events will be reported to the site IRB, the Data Safety Monitoring Board, the Sponsor and the NIH Program Office in a timely fashion, as specified in Section 7.

5.7. Subject withdrawal / Early termination

Subjects may voluntarily withdraw from the study at any time and for any reason, or this may be at the investigator's discretion. The investigator may withdraw a patient from the study due to protocol non-compliance, incorrect enrollment or randomization, or for any other reasons related to subject safety. The reason for study discontinuation will be recorded on the source documents and all such subjects will be asked to complete an early termination visit.

During this visit, we will document: (1) vital signs; (2) compliance with the medications, including pill count; (3) adverse effects, (4) specific reason for withdrawal.

Early Termination Visit Procedures

- Vital signs and physical exam
- Pill count and medication adherence log
- Safety labs
- Adverse event assessment
- Documentation of reason for withdrawal
- Retrieval of Aurora and Actigraph devices and data download

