Subjects that qualify for a 3T or 7T scanner (for the leg MRI study) also qualify for scanning in a 1.5T scanner (for the cardiac MRI substudy). However, the opposite is not necessarily true. Subjects who are determined eligible to undergo scanning in a 3T or 7T scanner (in the primary study) are eligible to undergo scanning in the 1.5T scanner (for the cardiac MRI study). Some situations (such as many intraluminal stents and prosthetic valves) which would exclude scanning at high field (7T or 3T) are considered safe for 1.5T scanning. Subjects who are deemed ineligible to undergo 7T or 3T scanning in the parent trial, may still be enrolled in the ancillary myocardial perfusion study and undergo a cardiac MRI study (at 1.5T). In all cases, participation in the myocardial perfusion / cardiac MRI ancillary study will be approved by [name], who has appropriate clinical expertise to assess the safety of this test, according to current clinical standards. [name] is the Director of Advanced Cardiac Imaging at the CMJC Philadelphia VA Medical Center and Assistant Professor at the University of Pennsylvania.

4.3.3. Criteria that will prompt exclusion from the trial at the 6 week visit

Subjects will be discontinued from study participation if they meet any of the following criteria at the 6-week study visit:

- 1. Acute coronary syndrome or coronary intervention for unstable coronary disease after enrollment
- New onset ischemia on stress testing since the time of enrollment, including clinically significant reversible ischemia in a coronary distribution identified during the cardiac MRI substudy.
- 3. New treatment with organic nitrates or phosphodiesterase inhibitors that cannot be withheld
- 4. Serum K>5.5 mEq/L
- 5. Any medical condition that, in the opinion of the investigator, will interfere with the safe completion of the study, or the validity of endpoint assessments. Although the ultimate authority/decision making will rely on each site PI, these ad-hoc discontinuations will be discussed with the other site PIs, the chair of the trial and the medical director of the IND for input.

Subjects who meet the criteria below will not be immediately discontinued, but will be scheduled for an ad hoc additional visit for reassessment of values prior to drug initiation in phase 2:

- 1. Supine systolic blood pressure <90 mm Hg
- 2. Acute kidney injury with eGFR < 30 mL/min/1.73m2
- 3. Methemoglobinemia baseline methemoglobin level >5%

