10.2. Data Analysis Plan

The co-primary outcome variables will be peak VO₂ and work performed during a symptom-limited maximal effort exercise test. All secondary outcome measures are continuous variables. The predictor of interest for all aims will be intervention (KNO₃ therapy vs. placebo), with analyses based upon the total number of subjects randomized. Initial descriptive estimates of all measures will be generated for study participants at each time point by treatment group. Statistics will include estimates of central tendency, measures of variability, and derived moments of skewness and kurtosis. Analyses of distributional properties will be performed to determine if variance stabilizing or normalizing transformations should be applied. Outliers will be assessed via visual inspection of distributions and checked for accuracy. Aim 1 will assess the effects of potassium nitrate therapy on peak O_2 / work performed (co-primary outcomes) and quality of life score (secondary outcome). An initial assessment of the treatment effect will be performed using the paired t-test and the non-parametric Wilcoxon sign-rank test on the difference between the paired within subject outcome measures. This will be followed by a more comprehensive linear mixed-effects model analysis¹⁵⁸ allowing for assessments of the treatment effect on each continuous outcome of interest while controlling for effects of other covariates such as period, sequence, and a random subject effect nested within sequence. For non-normal distributed outcomes, we will utilize nonparametric methods or consider distribution-stabilizing transformations. The intervention groups will initially be compared within each period (time invariant covariates will only be compared for period 1) according to continuous covariates described above using parametric or non-parametric one-way ANOVA models, depending upon whether or not normality appears to be in question. Levine's tests will be used to assess homogeneity of variance. Additionally, the intervention groups will be compared within period according to categorical covariates using Fisher's Exact tests. Significant differences between groups on these variables will result in their use as control variables in the modeling of outcome. Separate models will be generated for each of the two outcome measures, with each outcome measure regressed on intervention group assignment, along with baseline outcome and any other covariates deemed prognostic in preliminary analyses. The linear mixed-effects models will incorporate adjustments for any period effect and include data from dropouts.¹⁵⁹⁻¹⁶¹ The model will include subject-specific intercepts as random effects, and assumes independent and identically distributed random errors within subject. Restricted maximum likelihood estimation will be used, and an appropriate covariance matrix will be specified. Model assumptions will be examined (eg,QQ plots to assess normally distributed residuals for valid Wald tests). All mixed-effects models will be analyzed using the SAS PROC MIXED procedure¹⁶² in SAS version 9.3 (SAS Institute, Inc., Cary, NC). We will make every possible effort to minimize missing data and ensure final assessments for participants opting to discontinue study participation. Missing data, however, is an inevitable problem in a longitudinal study. The mechanism for missingness-missing completely at random (MCAR), missing at random (MAR), nonignorable or not missing at random (NMAR)-will be evaluated prior to implementing methodology intended to minimize bias from missing data.¹⁶³ We anticipate that ~10% of randomized subjects will not complete the study.

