
The intent-to-treat principle of including all randomized participants in the outcome models will be followed. SAS software procedures will be used for creating and analyzing multiple imputed data sets for incomplete multivariate data. Instead of filling in a single value for each missing value, Rubin's¹⁶⁴ multiple imputation procedure replaces each missing value with a set of plausible values that represent the uncertainty about the correct value to impute. These multiple imputed data sets are then analyzed using standard procedures for complete data and combining the results from this analysis. Assuming monotone missing data patterns emerge, either a parametric regression method that assumes multivariate normality or a nonparametric method that uses propensity scores will be implemented, depending upon distributional patterns.

Analytic methods described above will take advantage of all available data. The possibility of systematic bias in the outcomes for those who withdraw exists. Baseline characteristics will be compared among subjects with and without complete follow-up, recognizing that statistical power associated with finding true statistical differences may be limited. To assess potential biases, a comparison of withdrawal rates and or/time to withdrawal will be included. If the number of subjects lost to follow-up is small and the missing observations can be documented as being MAR or MCAR, then the primary hypotheses will be tested using the complete observed data. If missing observations cannot be assumed to be MAR or MCAR, more complex approaches will be considered. Sensitivity analyses for these models will be performed should they be implemented.¹⁶⁵

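### Section 5.7 lets investigators end a randomized subject's follow-up for non-compliance or an enrollment or randomization error, which undercuts the all-randomized analysis in section 10.2

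*Combined protocol and SAP*

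**What the plan says.** **Conduct.** Section 5.7 gives the investigator this power: "The investigator may withdraw a patient from the study due to protocol non-compliance, incorrect enrollment or randomization". The same sentence goes on to add further safety-related reasons, and the sentence before it allows withdrawal at the investigator's discretion in general. The protocol does not separate stopping the capsules from ending follow-up. Withdrawn subjects are asked to attend an early termination visit that documents vital signs and "compliance with the medications, including pill count; (3) adverse effects, (4) specific reason for withdrawal". Its procedure list adds a physical exam, safety labs and device download. It lists no exercise test and no KCCQ.

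Section 4.3.3 item 5 is a separate rule for the 6-week visit. It covers a medical condition that, in the investigator's opinion, "will interfere with the safe completion of the study, or the validity of endpoint assessments". The site PI decides, but "these ad-hoc discontinuations will be discussed with the other site PIs", the trial chair and the IND medical director.

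**Analysis.** Section 10.2 describes the comparison of treatments "with analyses based upon the total number of subjects randomized" and adds: "The intent-to-treat principle of including all randomized participants in the outcome models will be followed". It also says: "The linear mixed-effects models will incorporate adjustments for any period effect and include data from dropouts". Multiple imputation, a comparison of subjects with and without complete follow-up, and sensitivity analyses are described. The team further undertakes to "ensure final assessments for participants opting to discontinue study participation". That undertaking names subjects who choose to leave and does not mention those whom the investigator withdraws. The same section begins with paired tests on within-subject differences. It allows the primary hypotheses to be tested on the observed data alone if few subjects are lost and the losses can be taken as MAR or MCAR.

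**The concern.** An intent-to-treat comparison needs outcomes that are collected whether or not the subject adhered. Section 5.7 allows follow-up to end because the subject did not adhere, or because of an administrative error at entry. In an AB/BA crossover, ending follow-up before the second endpoint visit also breaks the within-subject pair on which the design relies.

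Non-compliance may not be balanced between treatments. Section 7.2 lists dizziness, headache and stomach symptoms among the expected effects of KNO₃, and such symptoms can lower adherence even under blinding. What is at stake is whether the reported effect on peak VO₂ and total work describes everyone randomized or mainly those who took their capsules.

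**Working it through.** **Step 1: where the co-primary endpoints are measured.**

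| Contact | Section | Maximal exercise test |
|---|---|---|
| Initial visit | 5.1 | No (6-minute walk only) |
| Phase 1, 6 weeks | 5.3 | Yes |
| Phase 2, 6 weeks | 5.5 | Yes |
| Early termination | 5.7 | No |

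**Step 2: what a removed subject contributes.**
- Removed during phase 1: no value for peak VO₂ or work. The subject adds nothing to the likelihood for either endpoint, and imputation has no earlier exercise test from that subject to draw on.
- Removed between phases: one value. The paired t-test and signed-rank test drop the subject. The mixed model can use the single value only through between-subject information.
- Non-adherence found only at the final visit: both endpoints are due by then, so no pair need be lost.

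**Step 3: possible size of the shift.** Inputs from section 10.1 are an effect of 0.6 ml/kg/min and an SD of change of 1.23. The plan's standardized effect reproduces: 0.6/1.23 = 0.488, stated as 0.49. The non-adherent fraction on KNO₃, f, is not in the documents. I assume 5%, 10% and 15%, and take 0.6 as the effect in adherent subjects.

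- (a) No benefit in non-adherent subjects, all removed: all-randomized effect = 0.6 × (1 − f).
- (b) Half benefit, all removed: all-randomized effect = 0.6 × (1 − f/2).
- For (a) and (b): overstatement = 0.6 / (all-randomized effect) − 1.
- (c) As (a), but only KNO₃-first subjects lose their pair. The scheduled pill count falls at each 6-week visit, so in the KCl-first sequence KNO₃ non-adherence found by that count emerges at the final visit. With equal sequences the estimate is [0.6 + 0.6 × (1 − f)]/2, compared with 0.6 × (1 − f).

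| f | (a) effect | (a) overstatement | (b) effect | (b) overstatement | (c) estimate | (c) overstatement |
|---|---|---|---|---|---|---|
| 5% | 0.570 | 5.3% | 0.585 | 2.6% | 0.585 | 2.6% |
| 10% | 0.540 | 11.1% | 0.570 | 5.3% | 0.570 | 5.6% |
| 15% | 0.510 | 17.6% | 0.555 | 8.1% | 0.555 | 8.8% |

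All three columns assume that the model and imputation correct nothing. Detection earlier in a phase, for example at the 1-week call, would move (c) back toward (a).

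**Step 4: precision.** SE = 1.23/√pairs: 0.134 at 84 pairs, 0.141 at 76, 0.149 at 68. The plan already budgets for 90% retention (84 × 0.9 = 75.6, about 76). Only losses beyond that are extra, and going from 76 to 68 pairs widens the SE by √(76/68) − 1 = 5.7%.

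Power is not the issue under the stated SD. A paired t-test with d = 0.49 and 76 pairs has 98.8% power, and 97.7% with 67 pairs. The plan's 80% does not reproduce, but the discrepancy is on the conservative side and is a separate matter. If 1.23 were a within-subject SD, so that differences have SD 1.23 × √2, power would be 84.7% at 76 pairs and 79.8% at 67.

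**The case against.** The strongest reply is that leaving the study is not leaving the analysis. Neither 5.7 nor 4.3.3 removes anyone from an analysis set, and section 10.2 keeps all randomized subjects, includes dropout data and plans imputation and sensitivity analyses. This stands, and it is why a reader who infers a formal contradiction goes too far. It does not supply the missing exercise tests. Imputation under MAR would draw largely on retained subjects, so the all-randomized effect would be modelled where it could have been observed.

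Other points on that side also stand in part:
- Mild symptoms need not lead to removal. Sections 5.3 and 5.5 let the site PI reduce the dose and keep the subject in the trial, which weakens the path from side effects to withdrawal.
- Protocol non-compliance need not mean missed capsules, and the wording of 5.7 could be read as tying its listed grounds to safety. That ambiguity is itself a reason to reword.
- Only the non-compliance ground selects on adherence. Removal for an enrollment or randomization error has no known direction of bias.
- The 15% case exceeds the roughly 10% non-completion from all causes that section 10.2 expects, and 5.7 permits removal without requiring it.

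A reader might also infer that section 4.3.3 item 5 lets a site drop subjects because of their phase 1 result. The documents do not support that. The item requires a medical condition and consultation beyond the site, allocation is blinded, and quantification is offline and blinded to treatment (8.1). No section places the decision after the test, and one period's value does not reveal the within-subject difference.

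**Conclusion.** The point holds as a gap between conduct and analysis. Section 5.7 permits follow-up to end for reasons that are not in themselves safety reasons. The co-primary endpoints are not measured outside the two 6-week visits, and the undertaking on final assessments leaves out investigator-withdrawn subjects. The all-randomized analysis would then rest on MAR modelling, imputation or complete pairs.

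The estimate can be too large; the documents do not show that it will be. The figures of 5%, 11% and 18% are upper bounds. They rest on assumed non-adherence of 5%, 10% and 15%, no benefit in those subjects, removal of all of them, and no correction by the model. With half benefit they fall to 3%, 5% and 8%. If only KNO₃-first subjects lose their pair, they are 3%, 6% and 9%.

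It would also be wrong to conclude that wrongly enrolled subjects must continue treatment. That is a clinical decision, and this point takes no position on it.

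**What to change.** In section 5.7, remove protocol non-compliance and incorrect enrollment or randomization, on their own, as grounds for ending study follow-up. State that, whatever is decided about study drug on safety or clinical grounds, such subjects:
- are asked to attend the scheduled 6-week endpoint assessments where this is safe;
- are analysed in the sequence to which they were randomized;
- have the deviation recorded.

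In section 10.2, extend the undertaking on final assessments to subjects withdrawn by the investigator. This also covers withdrawals under the general discretion in 5.7. Reconcile the two sections so that stopping drug and ending follow-up are distinct. Leave all safety grounds, decisions on stopping drug and section 4.3.3 item 5 unchanged. Whether endpoint validity should stay as a ground in item 5 is a debatable trade-off, and this fix does not depend on it.

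The cost is a short amendment that uses visits already scheduled. The downside is that poorly adherent subjects may slightly dilute the effect estimate.
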